3.3 Pharmacodynamic Analysis

3.3.1 Serum Testosterone Concentrations

Analysis Set:	Full Analysis Set		
Analysis			
Variable(s) :	Serum Testosterone Concentrations (ng/mL)		
Visit :	Baseline, D2, D3, D7, D14, D21, D28, D31, D35		
Analytical			
Method(s) :	The following analysis will be performed using the full analysis set.		
	For observed values and percent change from baseline, descriptive statistics		
and two-sided 95% confidence intervals of the mean will be provided t			
each visit by treatment group. Case plots as well as the mean and stand			
deviation plots of changes over time will be provided for observed va			
	each treatment group. A reference line will be drawn where the serum		
	testosterone concentration is 0.5 ng/mL.		

3.3.2 Serum Concentrations of LH, FSH, DHT, and SHBG

Analysis Set:	Full Analysis Set		
Analysis			
Variable(s) :	(1) Serum Concentrations of LH (mIU/mL)		
	(2) Serum Concentrations of FSH (mIU/mL)		
	(3) Serum Concentrations of DHT (ng/mL)		
	(4) Serum Concentrations of SHBG (nmol/L)		
Visit :	Baseline, D2, D3, D7, D14, D21, D28, D31, D35		
Analytical			
Method(s) :	The following analysis will be performed using the full analysis set.		
	For the analysis variables (1) to (4), descriptive statistics of the observed		
	values and the two-sided 95% confidence intervals of the mean will be		
	provided for each visit by treatment group. The same analysis will be		
	performed for the percent change from baseline. Case plots as well as the		
	mean and standard deviation plots of changes over time will be provided for		
	observed values for each treatment group.		

3.4 Statistical/Analytical Issues

3.4.1 Adjustments for Covariates

Not applicable in this study.

3.4.2 Handling of Dropouts or Missing Data

Missing test results and data determined to be non-evaluable according to the Handling Rules for Analysis Data will not be used for hypothesis testing and estimations.

Values less than or equal to the lower limit of quantification will be treated as the value of the lower limit of quantification for PSA, serum testosterone, LH, FSH, DHT, and SHBG, and all others will be treated as zero when calculating the descriptive statistics.

Values less than the lower limit of quantification will be treated as zero except for the calculation of geometric mean for plasma concentration of TAK-385. For the geometric mean, values less than the lower limit of quantification will be treated as missing.

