### 13.1.5 Pharmacodynamic Analysis

[Secondary endpoint]

Serum testosterone concentration

[Analytical method]

The full analysis set will be analyzed as follows.

1) Serum testosterone concentration

Descriptive statistics and the two-sided 95% confidence interval of the mean for serum testosterone concentration will be calculated by Part and by dose at each assessment time point specified in the protocol, and the changes over time (individual and mean/SD) will be graphed by Part and by dose.

2) Data conversion and handling of missing data

Test parameters below the lower limit of quantification will be handled as the LLOQ. Test data that is not assessed or that is missing, or that is not used per the "Rules for Handling Analytical Data," will be excluded from the analysis of assessment.

[Other endpoints]

Serum concentrations of LH, FSH, DHT, and SHBG

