2.3.2 Dosing Pattern Details

Analysis Set:	Safety Analysis Set	
Analysis		
Variable(s) :	Dosing Pattern	[80 mg,
		120 mg,
		80 / 120 mg,
		80 / 120 / 80 mg,
		80 / 40 mg,
		120 / 160 mg,
		120 / 160 / 120 mg,
		120 / 80 mg, etc.]
		*These categories are merely an
		example and may change in
		accordance with the actual data.
	Last Dose	[40 mg, 80 mg, 120 mg, 160 mg]
Analytical		
Method(s):	(1) Dosing Pattern Details	

Frequency distributions will be provided by treatment group and overall.

3 Efficacy, Pharmacokinetic, and Pharmacodynamic Analysis (Part A)

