4.4.2 Handling of Dropouts or Missing Data

Missing test results and data determined to be non-evaluable according to the Handling Rules for Analysis Data will not be used for hypothesis testing and estimations.

Values less than or equal to the lower limit of quantification will be treated as the value of the lower limit of quantification for PSA, serum testosterone, high-sensitivity serum testosterone, LH, FSH, DHT, and SHBG, and all others will be treated as zero when calculating the descriptive statistics.

Values less than the lower limit of quantification will be treated as zero for the calculation of descriptive statistics except for geometric mean for plasma concentration of TAK-385. For the geometric mean, values less than the lower limit of quantification will be treated as missing.

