6.3.1.2 Urinalysis

Analysis Set: Safety Analysis Set Analysis Variable(s) : pH

	-	
	Specific Gravity	
	Protein	[-, +-, 1+, 2+, 3+, 4+, 5+]
	Glucose	[-, +-, 1+, 2+, 3+, 4+, 5+]
	Occult blood	[-, +-, 1+, 2+, 3+, 4+, 5+]
	Ketones	[-, +-, 1+, 2+, 3+, 4+, 5+]
	Urobilinogen	[-, +-, 1+, 2+, 3+, 4+, 5+]
	Bilirubin	[-, +-, 1+, 2+, 3+, 4+, 5+]
Categories:	Intensity	[Grade 0, Grade 1, Grade 2, Grade 3, Grade 4]

Visit:	(1), (2), and (3):
	Baseline, WK5D1, WK9D1, WK13D1, WK25D1, WK49D1, WK61D1,
	WK73D1, WK85D1, WK97D1, SFU

Analytical

Anarytical			
Method(s) :	For pH and specific gravity, summaries (1) and (2) will be provided by		
	treatment group.		
	For each variable other than pH and specific gravity, summary (3) will be		
	provided by treatment group.		
	For protein, summaries (4) and (5) will also be provided by treatment group.		
	(1) Summary of Urine Laboratory Test Results and Change from Baseline		
	by Visit		
	Descriptive statistics for observed values and changes from baseline		
	will be provided for each visit.		
	(2) Case Plots		
	Plots over time for each subject will be presented.		
	(3) Number of Subjects in Categories of Urine Laboratory Test Results		
	Shift tables showing the number of subjects in each category at baseline		
	and each post-baseline visit will be provided.		
	(4) Number and Percentage of Subjects with Urine Laboratory Test		
	Abnormalities by Grade		
	Frequency distributions for each urine laboratory test abnormality will		
	be provided by grade. Evaluable data (i.e., non-missing and acceptable		
	according to the Handling Rules for Analysis Data) obtained after		
	baseline will be used. A subject with multiple occurrences of laboratory		
	test abnormality will be counted once for the abnormality with the		
	maximum intensity.		
	(5) Maximum Grade Shift From Baseline of Urine Laboratory Parameters		
	The maximum post-baseline grade will be determined for each subject.		
	Shift tables showing the number of subjects in each grade category at		
	baseline and post-baseline visit will be provided using evaluable data		
	(i.e., non-missing and acceptable according to the Handling Rules for		
	Analysis Data).		

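### SAP 3.4.2 and 4.4.2 turn a measured result equal to the LLOQ into zero for every assay outside the PSA and hormone list, and leave it unclear whether safety laboratory tests are included

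*SAP*

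**What the plan says.** SAP 3.4.2 (Part A) opens its quantification-limit rule with "Values less than or equal to the lower limit of quantification will be treated as the value of the lower limit of quantification for PSA". It then adds serum testosterone and closes with "LH, FSH, DHT, and SHBG, and all others will be treated as zero when calculating the descriptive statistics". The at-or-below condition at the start governs both halves of the sentence.

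SAP 4.4.2 (Part B) uses the same construction with one assay added to the list: "high-sensitivity serum testosterone, LH, FSH, DHT, and SHBG, and all others will be treated as zero when calculating the descriptive statistics".

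In each section the next paragraph deals with plasma drug concentration under a different condition. In Part A it reads "Values less than the lower limit of quantification will be treated as zero except for the calculation of geometric mean for plasma concentration of TAK-385". Such values count as missing when the geometric mean is computed.

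The protocol is narrower. Its section 13.1.5 says "Test parameters below the lower limit of quantification will be handled as the LLOQ", and 13.1.3 has the equivalent for PSA. Both apply strictly below the limit. The protocol gives no such rule for safety laboratory tests.

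SAP 5.3.1 and 6.3.1 summarise hematology, biochemistry, lipids and HbA1c, and two urine variables, by descriptive statistics of the observed value and the change from baseline. Neither section mentions an LLOQ. The SAP glossary defines descriptive statistics as n, mean, SD, maximum, minimum and quartiles.

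**The concern.** An assay result equal to the LLOQ is, by the meaning of the term, a quantified result. For PSA and the hormones the at-or-below wording does no harm, because the LLOQ is replaced by itself. For everything else it discards a valid observation and enters zero.

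Clinical laboratory tests are a primary endpoint in both parts (Protocol 5.2.1). Groups are small: 3 or 6 men per cohort in Part A and 15 per group in Part B (Protocol 13.3). If the zero rule covers these tests, one man at a limit moves the mean, SD and minimum of his group. He also acquires a false change from baseline whenever he moves onto the limit or off it.

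The scope is a second problem. Two programmers could reasonably differ on whether the sentence applies to safety laboratory data at all.

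**Working it through.** The plan states no figure on this point, so there is nothing to reproduce. The check has two parts.

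**Scope, by comparing the sections**

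1. PSA and the listed hormones are named and take the LLOQ, so they are outside the zero clause.
2. Plasma TAK-385 has its own paragraph. The amendment log in SAP Appendix 1 shows that paragraph as new in version 2.
3. The other variables in chapters 3 and 4 are QOL scores, imaging progression and rates, none of which has an LLOQ. If plasma is governed by its own paragraph, the residual category has nothing left to cover in those chapters. That points towards the laboratory tests.
4. Chapters 5 and 6 contain no LLOQ rule and no exemption.
5. Against this, 3.4.2 and 4.4.2 belong to the efficacy, pharmacokinetic and pharmacodynamic chapters and name no safety laboratory variable.

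The literal reading therefore includes safety laboratory tests, but this is an inference.

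**Conflict for plasma TAK-385.** For a concentration exactly at the LLOQ, the first sentence (at or below, all other assays) gives zero in the arithmetic mean. The following paragraph (strictly below) leaves the value as measured.

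**Arithmetic where the zero rule applies.** Inputs: n from Protocol 13.3. The number affected, k, and the starting values are assumed, and results are in units of one LLOQ.

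- Shift in group mean = (sum with zeros − sum as measured)/n = −(k/n) × LLOQ, for k results exactly at the LLOQ.
  - n = 3, k = 1: −1/3 = −0.333
  - n = 6, k = 1: −1/6 = −0.167
  - n = 15, k = 1: −1/15 = −0.067
  - n = 15, k = 3: −3/15 = −0.20
- One man, baseline 1.5, later result exactly 1.0: change as measured 1.0 − 1.5 = −0.5; under the zero rule 0 − 1.5 = −1.5.
- Fifteen men at baseline 1.5, three of whom fall to exactly 1.0 while the rest do not change:
  - as measured: mean change 3 × (−0.5)/15 = −0.10, SD 0.207, minimum observed value 1.0
  - zero rule: mean change 3 × (−1.5)/15 = −0.30, SD 0.621, minimum observed value 0

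In that last case both the mean change and its SD are three times what was measured.

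For a concrete scale, assume a total bilirubin LLOQ of 0.2 mg/dL and three men at 0.2, 0.5 and 0.7. The mean as measured is 1.4/3 = 0.467. With the zero it is 1.2/3 = 0.400, a fall of 0.067/0.467 = 14%.

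**The case against.** The strongest reply is about placement. The sentence lies outside the safety chapters, which do not refer back to it. The plasma paragraph was added in version 2, and the log records no change to the sentence before it, so the zero clause may simply be the old plasma rule left behind. On that reading the SAP has no LLOQ rule for safety laboratory tests, which is a gap and not a zero rule. This cannot be excluded, and it is why the scope is described here as uncertain. It does not rescue the wording: either a primary endpoint has no rule, or it has a wrong one, and on both readings the plasma conflict remains.

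The SAP also relies on separate Handling Rules for Analysis Data, which are not among the documents. They might settle the matter, but nothing in the SAP says that they do.

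Setting low values to the LLOQ is itself only a convention and carries its own bias. That is true. It is, however, the convention already used for PSA and the hormones, and it leaves a value at the limit intact.

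A reader might go further and infer three things that the documents do not support:

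- That every laboratory value at or below its limit becomes zero. The same sentence exempts PSA, testosterone and the other listed hormones.
- That urine pH and specific gravity would take impossible values, since the SAP treats them as continuous ("For pH and specific gravity, summaries (1) and (2) will be provided by" treatment group). No LLOQ is given for either, and the lowest reading on a scale is not shown to be one.
- That limits differ between sites. Protocol 9.1.8 says only that testing is done at the medical institution.

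**Conclusion.** The point holds in a limited form. The at-or-below condition combined with the zero clause gives a wrong value for any result equal to the LLOQ outside the named list, and it contradicts the plasma paragraph at that value. Read literally it reaches the safety laboratory summaries, though the chapter placement leaves this open.

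The error in a group mean is (k/n) × LLOQ for k results exactly at the limit: one third of an LLOQ for one man in three, one fifteenth for one man in fifteen. For results below the limit, the same expression is the difference from the LLOQ convention, not from the unknown true value. The documents give no LLOQs and no frequency of such results, so the actual size is unknown, and it is nil if no result reaches a limit.

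It would be too much to conclude that the primary safety assessment rests on false data. The clause is confined to descriptive statistics. By its wording it does not alter the CTCAE grade tables and shifts, the elevated-liver-enzyme counts or the DLTs, and the plan bases no hypothesis test on a laboratory mean. The correction should be made because a stated rule is wrong and costs almost nothing to put right.

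**What to change.** In SAP 3.4.2 and 4.4.2:

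1. Change the condition to strictly below the LLOQ, so that a result equal to the LLOQ is used as measured.
2. Delete the clause that sets all other variables to zero.
3. State that clinical laboratory values below the LLOQ are set to the LLOQ, as for PSA and the hormones, and that the number of such values is reported.
4. Leave plasma TAK-385 to its own paragraph, unchanged.

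A cross-reference from SAP 5.3.1 and 6.3.1 would remove the doubt about scope.

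Cost: one sentence in each of two sections, a small programming change and a count in the laboratory tables. No new data are needed.

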3.4.3 Interim Analyses and Data Monitoring

No interim analysis is planned in this study.

3.4.4 Multicenter Studies

Although this study is a multicenter study, treatment-by-center interaction will not be explored since the number of subjects for each center is not sufficient for such exploration.

3.4.5 Multiple Comparison/Multiplicity

Not applicable in this study.

3.4.6 Use of an "Efficacy Subset" of Subjects

Not applicable in this study.

3.4.7 Active-Control Studies Intended to Show Equivalence or Non-Inferiority

Not applicable in this study.

3.4.8 Examination of Subgroups

Not applicable in this study.

4 Efficacy, Pharmacokinetic, and Pharmacodynamic Analysis (Part B)

4.1 Efficacy Analysis

4.1.1 Antitumor Effects

Analysis Set:	Full Analysis Set		
Analysis			
Variable(s) :	(1) PSA (ng/mL)		
	(2) Rate of Progression Based on PSA (%)		
	(3) Rate of Progression Based on Imaging Assessments (%)		
Visit :	(1) Baseline, WK5D1, WK9D1, WK13D1, WK17D1, WK21D1, WK25D1,		
	WK37D1, WK49D1, WK61D1, WK73D1, WK85D1, WK97D1,		
	WK13D1 (LOCF), End of Study		
	(3) WK49D1, WK97D1		

Analytical

Method(s): The following analysis will be performed using the full analysis set.
(1) For the observed values, descriptive statistics and two-sided 95% confidence intervals of the mean will be provided for each visit by treatment group. Case plots as well as the mean and standard deviation plots of changes over time will be provided for each treatment group. The same analysis will be performed for the percent change from baseline.

The percent change from baseline at WK13D1 (LOCF) as well as the percent change from baseline when the PSA value is at its minimum since the start of the study drug administration will be shown using waterfall plots for each treatment group.

(2) Rate of progression based on PSA will be defined as the proportion of subjects who have a 25% or greater increase as well as an absolute increase of 2 ng/mL or more in the value of PSA at least 4 weeks from the nadir. If the value of PSA never decreased from baseline, the above conditions will be fit to the value obtained after WK13D1. A missing value will be assigned if neither of the following conditions is met: "there are at least two observations after study drug administration" or "there is at least one observation on or after WK13D1 and the baseline is not missing". If the same minimum PSA value occurs at several visits, then the PSA value with the earliest date will be used as the nadir. Frequency distributions will be provided for each treatment group.

(3) Rate of progression based on imaging assessments will be defined as the proportion of subjects who have developed new lesions. Frequency distributions will be provided for each visit by treatment group.

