Cohort 4 will be conducted after tolerability is confirmed in Cohort 2. Cohort 4 will be conducted for the purpose of evaluating the tolerability of 360 mg as loading dose in Japanese. 360 mg has been found tolerable in single dosing in the overseas phase 1 single-/multiple-dose study (TAK-385\_C27001) [REDACTED].

[figure not shown]
In Part B, subjects will be randomized to receive study drug (TAK-385 loading dose of 320 mg and maintenance dose of either 80 mg or 120 mg – equal numbers of subjects will be randomized to 80 mg and 120 mg) once a day orally to evaluate safety. In addition to the safety assessments, efficacy assessments will also be performed according

to the study schedule, and study drug will be administered until the discontinuation criteria (Section 7.5) are met for each individual subject. After completing 48 weeks of treatment, subjects may, at the discretion of the investigator, and depending on the wished of the subject, continue receiving study drug (for a maximum of 96 weeks), or they may complete the study and be switched to a GnRH agonist (eg, leuprorelin) or a GnHR antagonist (eg, degarelix), starting from the day after the day of the last dose of TAK-385. Subjects withdrawing from the study will not be replaced.

If no problems with tolerability are found in the additional cohort in Part A, then the study will proceed to Part B with a 40 mg group instead of a 120 mg group (TAK-385 loading dose of 320 mg and maintenance dose of 40 mg).

All subjects who receive study drug, whether in Part A or Part B, will undergo safety follow-up 30 to 40 days after the last dose of TAK-385.

[figure not shown]
Part A (Dose-rising phase)

\*1: If tolerability is not confirmed in Cohort 2, then a cohort will be added which will receive a loading dose of 320 mg and a maintenance dose of 40 mg.

\*2: If a cohort is added, and the additional cohort continues to the end and no problems with tolerability are found, then the study will proceed to Part B.

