## 6. Lack of efficacy

This will be considered the primary reason for withdrawal if the expected level of efficacy is not obtained because of disease progression assessed by PSA level or evaluation of soft tissue or bone lesions by diagnostic imaging (according to the Prostate Cancer Handling Guidelines, Fourth Edition [16]), or if the decrease in serum testosterone meets any of the following criteria.

- 1) If, in Part A, serum testosterone does not drop below 50 ng/dL at 2 or more time points at least 7 days apart following treatment initiation, and it is determined as a result that the patient must be switched to some other therapy.
- 2) If, in Part B, serum testosterone does not drop below 50 ng/dL by 4 weeks after uptitration based on the uptitration criteria (see Section 8.1.3.1).
- 3) If, in Part B, serum testosterone exceeds 50 ng/dL on 2 consecutive occasions, or on 3 occasions in total, whether consecutive or not, by 9 weeks (57 days) after the start of treatment following uptitration in accordance with the uptitration guidelines (see Section 8.1.3.1).

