#### 9.1.10 Tumor Marker

PSA will be measured by a third-party organization according to a separately prepared written procedure. Progression of disease as indicated by PSA (based on the Prostate Cancer Handling Guidelines, 4th Edition [16]) is defined as an increase of at least 25% in the PSA value measured at least 4 weeks after the minimum PSA value measured during the study period (at least 12 weeks if the minimum value was recorded during screening). In such a case, the amount of increase must be at least 2 ng/mL. The date this condition is met will be considered the disease progression date.

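### SAP 4.1.1(2) reports Part B PSA progression as a crude proportion with no time horizon, so it estimates neither a 48-week nor a 96-week risk and depends on who continues past Week 48

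*SAP*

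**What the plan says.** SAP 4.1.1 (Part B), variable (2), gives the definition: "Rate of progression based on PSA will be defined as the proportion of subjects who have a 25% or greater increase". The rise must also be an "absolute increase of 2 ng/mL or more in the value of PSA at least 4 weeks from the nadir". If PSA never fell from baseline, only values obtained after WK13D1 can qualify. The output is one frequency distribution per treatment group. The Visit field lists visits for PSA values (1) and for imaging progression (3, at WK49D1 and WK97D1), but none for (2).

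On missing data the same section says: "A missing value will be assigned if neither of the following conditions is met". The two conditions are "there are at least two observations after study drug administration" and "there is at least one observation on or after WK13D1 and the baseline is not missing". A man is therefore set to missing only if both fail.

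Protocol 6.1 lets men who complete 48 weeks "continue receiving study drug (for a maximum of 96 weeks), or they may complete the study" and switch therapy. Protocol 9.1.10 defines an event time: "The date this condition is met will be considered the disease progression date". SAP 4.1.1(2) does not use that date.

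**The concern.** A proportion of men who ever progressed has a clear meaning when everyone is observed for the same time. Here observation differs by design. PSA is scheduled to WK97D1 for men who continue and stops at WK49D1 for those who finish. It is not among the safety follow-up assessments in Protocol 9.3.8, so a leaver's later PSA status is not collected. Even so, he is scored as a man who did not progress.

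The figure therefore mixes the progression hazard with the share who continue. Two dose groups with the same hazard can show different rates because different numbers stayed on after Week 48. A reader who takes the figure as a 48-week risk will tend to overstate that risk. A reader who takes it as a 96-week risk will tend to understate it. Neighbouring endpoints do not have this gap: imaging progression is reported at two named visits, and the castration rate in SAP 4.3.1 has a fixed window (WK5D1 to WK25D1) and a 95% CI.

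**Working it through.** **The plan's own figure.** No rate, event count or precision is stated for PSA progression. The only Part B figure is in Protocol 13.3: 15 men per group give about an 80% chance of seeing an AE with true incidence 10%. This reproduces: 1 − 0.9^15 = 0.794. It fixes the group size used below.

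**Who counts as a non-progressor.** Post-dose PSA is scheduled at WK5D1, WK9D1, WK13D1 and onward (Protocol Appendix B).

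| Man without observed progression | Treatment under SAP 4.1.1(2) |
|---|---|
| Leaves with fewer than two post-dose values, and no baseline plus a value on or after WK13D1 | Missing |
| Leaves after the second post-dose value (WK9D1 on schedule) | Non-progressor |
| Finishes at Week 48 with those values | Non-progressor |
| PSA never fell, only WK5 and WK9 values | Non-progressor; the first condition is met, but the criterion applies only after WK13D1, so he could not have qualified |

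A man who meets the criterion before or at withdrawal counts as a progressor. PSA is scheduled at the withdrawal visit.

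**Size with no early withdrawal.** Assumptions: constant hazard, 48-week risk r, and a share f of unprogressed men continuing to Week 96.

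Crude rate = r + (1 − r) × f × r; 96-week risk = 1 − (1 − r)².

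| r | f | Crude rate | 96-week risk |
|---|---|---|---|
| 10% | 25% | 0.10 + 0.90 × 0.25 × 0.10 = 12.2% | 19% |
| 10% | 50% | 0.10 + 0.90 × 0.50 × 0.10 = 14.5% | 19% |
| 10% | 75% | 0.10 + 0.90 × 0.75 × 0.10 = 16.7% | 19% |
| 20% | 25% | 0.20 + 0.80 × 0.25 × 0.20 = 24% | 36% |
| 20% | 75% | 0.20 + 0.80 × 0.75 × 0.20 = 32% | 36% |

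The last two rows have the same hazard. The 8-point gap comes only from continuation.

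**Size with early withdrawal and the missing rule applied.** Assumptions: constant progression and withdrawal hazards, with men who withdraw unprogressed before Week 8 set to missing. For a 96-week risk of 20%, the 48-week risk is 1 − √0.80 = 10.6%.

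| Share leaving at Week 48 | 0% | 25% | 50% | 75% | 100% |
|---|---|---|---|---|---|
| Crude rate, no earlier withdrawal | 20.0% | 17.6% | 15.3% | 12.9% | 10.6% |
| Crude rate, 20% withdrawn by Week 48 | 16.9% | 15.1% | 13.4% | 11.6% | 9.8% |

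In the second row about 3.6% of men are set to missing, so the missing rule changes little. Over early withdrawal of 0 to 20% and all leaving shares, the crude rate runs from 4.8% to 10.0% for a 96-week risk of 10%, and from 21.1% to 40.0% for a 96-week risk of 40%.

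**What a time-based estimate does with the same data (invented example).** In a group of 15, 2 men withdraw at WK17, 1 progresses at WK25, 8 leave at WK49, and 1 of the remaining 4 progresses at WK73. The SAP rate is 2/15 = 13.3%. Kaplan-Meier gives 1/13 = 7.7% at 48 weeks and 1 − (12/13) × (3/4) = 30.8% at 96 weeks.

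**The case against.** The plan nowhere says that this rate estimates a risk at 48 or 96 weeks. Protocol 5.2.3 lists it as an additional endpoint, Protocol 6.2 calls its purpose preliminary, and Protocol 13.1.3 names it without a method, so the SAP departs from nothing. No test or between-group comparison is planned. SAP 2.1.4 and 2.1.5 tabulate completion, extension entry and discontinuation reasons by group, and PSA itself is summarised at every visit with individual plots. An attentive reader could see unequal follow-up.

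The size is also small in men. One man is 1/15 = 6.7 points, and 24% against 32% is 3.6 against 4.8 men. An exact 95% CI for 2/15 is 1.7% to 40.5%. Every rate used above is assumed, and a constant hazard fits poorly with a definition that cannot be met in the first weeks. Kaplan-Meier has its own weakness: it assumes uninformative censoring, and after Week 48 it rests on men who chose to continue. In the example, one event among four men moves the estimate from 7.7% to 30.8%.

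Most of this stands, and it limits the severity. It does not give the percentage a meaning. The disposition tables show that follow-up differs but do not correct the rate, and a named horizon costs almost nothing.

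**Conclusion.** The point holds as a minor one. The PSA progression rate has no horizon. It equals the 96-week risk only if nobody leaves early. By design it equals the 48-week risk only if everyone leaves at Week 48 with no earlier withdrawal. Otherwise it depends on the share who continue. That follows from the text alone. The sizes (24% against 32%, or 10.6% to 20.0% for a 96-week risk of 20%) rest on assumed hazards and continuation shares.

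Two stronger readings are tempting but not supported. A reader might infer that every man who withdraws is scored as a non-progressor. The earliest leavers are set to missing, and men whose progression is seen before or at withdrawal count as progressors. A reader might also infer that men withdrawn because "serum testosterone does not drop below 50 ng/dL by 4 weeks after uptitration based on the uptitration criteria" (Protocol 7.5, item 6) are the likeliest to progress, so that a group with more of them would look better. That is plausible, but nothing in the documents shows it.

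**What to change.** In SAP 4.1.1(2), take the progression date from Protocol 9.1.10 and report by treatment group the Kaplan-Meier probability of PSA progression through WK49D1 with its 95% CI, censoring at the last evaluable PSA. Report WK97D1 as supplementary, with numbers at risk and a note that it rests on men who chose to continue. Keep the crude count as a descriptive line. State how a man is classified if his PSA never fell and he has no value late enough for the criterion to apply.

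The cost is a few lines of SAP text and one small table from data already collected. The downside is wide intervals with 15 men per group and reliance on uninformative censoring; both should be stated beside the table.
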